1. ABSTRACT/STUDY DIAGRAM

Most cocaine dependent patients suffer from deficits in cognitive function that, if left untreated, predict poor outcome.

Purpose: The present study investigates a pharmacotherapeutic intervention designed to improve cocaine treatment success by combining medications that act simultaneously on dopamine, the brain system that is critically associated with chronic cocaine use and cognitive functions. **Procedures:** Treatment with levodopa/carbidopa plus ropinirole (tested at two doses) will be compared to levodopa/carbidopa alone, and placebo. Measurement of performance on behavioral/cognitive measures of decision-making, behavioral inhibition, reward motivation, and attentional bias will be conducted at treatment entry and at repeated time points during the 10-week treatment. It is hypothesized that treatment with levodopa/carbidopa + ropinirole will produce superior outcomes in terms of reduced cocaine use and increased treatment retention and that these effects will occur indirectly via improved performance on observed cognitive mechanisms. **Course of Study:** Eligible cocaine dependent patients will be randomized equally to one of four medication conditions. Outpatient treatment will last 10 weeks and consist of thrice-weekly clinic visits. The behavioral therapy platform for this trial will consist of weekly cognitive behavioral therapy (CBT). The primary outcome measure will be weekly mean proportion of cocaine non-use days. Secondary endpoints will include abstinence rates during the last 2 weeks of treatment, time in study, and medication compliance. **Enrollment:** This project requires a final intent-to-treat sample size of 200 subjects. To obtain this sample, we expect to conduct phone screens on ~ 640 individuals, of whom 320 (50%) will qualify, enroll, and start intake. Of the 320 who start intake, we expect that 200 (~60%) will complete intake and be randomized into the ITT sample. Based on these projections and recruitment rates achieved during our previous levodopa studies, 40 months will be allotted to complete study enrollment (~ 5 new subjects/month).

Recruitment: Adult (18-55yo) men and women of all ethnic backgrounds will be recruited to participate. Participants will be non-hospitalized, self-referred persons who call in response to various advertising strategies, including newspaper/newsletter articles and announcements, public service announcements on television and radio, notices mailed to local professionals, city-wide billboards, and posters located throughout the local community. **Known Risks:** The known risks associated with the study medications (levodopa/carbidopa, ropinerole) include potential side effects but these are deemed minimal and will be clearly listed in the informed consent form. **Data Safety Monitoring:** This trial will adhere to general data and safety monitoring procedures. A DSM Board will be formed to provide additional, independent oversight of data related to patient safety. **IND#:** N/A. **Proposed Funding Source:** National Institute on Drug Abuse (NIDA). **Communication of Study Results:** Study results will be communicated at national scientific meetings and to all oversight entities, e.g., NIDA, IRB.

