6.4 MEDICATION DISPENSING

At each clinic visit (MWF) subjects will be administered the medication at the dispensing window and given take-home doses for intervening days. Riboflavin (50mg) will be added to the medication (and placebo) capsules and used as a marker to monitor compliance. We will use a double-dummy method involving a matched placebo for each of the two medications. Placebo capsules will be identical in size, color, coating and shape. Participants in all conditions will take the same number of capsules at the same scheduled times (morning/evening) per day throughout treatment. Participants in the single medication condition will take one matching placebo twice per day, at the same time they take their active study medication. Participants in the placebo group will take two matching placebos twice per day. This method, along with additional strategies used in our clinic to protect the integrity of blindness, will be applied.

Placebo + placebo

	Wk1	Wk2	Wk3	Wk4	Wk5	Wk6	Wk7	Wk8	Wk9	Wk10
L-dopa/carb	0	0	0	0	0	0	0	0	0	0
ropinirole	0	0	0	0	0	0	0	0	0	0
Total										
I-dopa/carb	0mg									
ropinirole	0 mg									
Morning dose	1 capsule placebo ; 1 capsule placebo									
Evening dose	1 capsule placebo ; 1 capsule placebo									
Total pills	4	4	4	4	4	4	4	4	4	4
	Run-up			Maintenance						Run-down

Comments: High dose condition (l-dopa/carbidopa + ropinirole 4 mg/d) has option to hold ropinirole dose at 2 mg/d if tolerability issues. Blood pressure monitoring at every clinic visit.

Levodopa-carbidopa 800/200 mg/d + placebo

	Wk1	Wk2	Wk3	Wk4	Wk5	Wk6	Wk7	Wk8	Wk9	Wk10
L-dopa/carb	200/50 x 2	400/100 x 2	400/100 x 2	400/100 x 2	400/100 x 2	400/100 x 2	400/100 x 2	400/100 x 2	400/100 x 2	200/50 x 2
ropinirole	0	0	0	0	0	0	0	0	0	0
Total L-dopa/carb	400/100 0 mg	800/200 0 mg	400/100 0 mg							
Morning dose	1 capsule containing 2-200/50 tablets; 1 capsule placebo									
Evening dose	1 capsule placebo; 1 capsule placebo	1 capsule containing 2-200/50 tablets; 1 capsule placebo	1 capsule containing 2-200/50 tablets; 1 capsule placebo	1 capsule containing 2-200/50 tablets; 1 capsule placebo	1 capsule containing 2-200/50 tablets; 1 capsule placebo	1 capsule containing 2-200/50 tablets; 1 capsule placebo	1 capsule containing 2-200/50 tablets; 1 capsule placebo	1 capsule containing 2-200/50 tablets; 1 capsule placebo	1 capsule containing 2-200/50 tablets; 1 capsule placebo	1 capsule placebo; 1 capsule placebo
Total pills	4									

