7.2.3 IN TREATMENT

During the 9-week treatment phase participants will be scheduled to attend three clinic visits per week (MWF). Activities conducted at these visits will include urine testing, administration of study medication, cognitive behavioral therapy, and prize-based CM for attendance. Brief (5-10 min) evaluations by the study nurse will be conducted weekly to address concerns related to side effects, concomitant medications, and general adherence to the medication regimen.

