7.2.5 END OF STUDY VISIT (WEEK 9)

At week 9, participants will be administered end of study assessments and given appropriate referrals to alternative treatment facilities in the area.

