8. ASSESSMENT SCHEDULE

STUDY 64		Admit week	1	2	3	4	5	6	7	8	9	10
Forms												
Study 64 consent form and quiz		X										
Medication information sheet		X										
Weekly Locator		X	X	X	X	X	X	X	X	X	X	X
Con Med		X	X	X	X	X	X	X	X	X	X	X
SUR (3xwk)		X	X	X	X	X	X	X	X	X	X	X
AIMS		X	X	X	X	X	X	X	X	X	X	X
AE		X	X	X	X	X	X	X	X	X	X	X
BDI-2		X										X
BSCS		X										X
SHAPS		X										
URICA		X										
DTCQ		X										
OCDUS		X	X	X	X	X	X	X	X	X	X	X
NART-2		X										
Shipley - 2		X										
Computerized Tests												
IGT-repeat version		X			X		X		X		X	
Risky Decision Making		X			X		X		X		X	
Continuous Performance Test		X			X		X		X		X	
Progressive Ratio (PR)		X			X		X		X		X	
Cocaine Stroop		X			X		X		X		X	
Reversal Learning		X			X		X		X		X	
Activities												
Blood draw				X		X		X		X		X
Preg				X		X		X		X		X
EKG		X		X		X		X		X		X
Vitals		X	X	X	X	X	X	X	X	X	X	X
BAL (3x/wk)		X	X	X	X	X	X	X	X	X	X	X
Urine rapid Test (3x/wk)		X	X	X	X	X	X	X	X	X	X	X
Fishbowl		X	X	X	X	X	X	X	X	X	X	X

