 $[\text{levodopa}/\text{carbidopa} + 4 \text{ mg/d ropinirole}] > [\text{levodopa}/\text{carbidopa} + 2 \text{ mg/d ropinirole}] > [\text{levodopa}/\text{carbidopa} + \text{placebo}] > [\text{placebo} + \text{placebo}]$. H1 will test for differential change over time as a function of treatment. H2 will test the ordinal relations of treatment effects as a follow-up analysis. As defined above (see Sect. B.3.2.5.ii) cocaine use will be measured by urine benzoylecgonine and by the SPRHK1 approach. Generalized linear mixed models will evaluate the probability of cocaine use as a function of time, treatment and their interaction. Logistic regression will evaluate retention, defined by completion of 12 weeks of treatment, as function of intervention condition. Proportional hazards regression will evaluate time to drop-out as a function of treatment. If differential attrition raises concerns regarding non-ignorable missingness, evaluation of cocaine use will implement pattern-mixture modeling. To evaluate the relative efficacy of the treatment conditions we will follow up the omnibus test with ordinal contrasts.

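### The SAP's 12-week retention definition cannot be met on a schedule that ends at week 10, and the same conflict over treatment length leaves the abstinence endpoint with two possible windows

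*Protocol*

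**What the plan says.** The documents give three treatment lengths.

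- **Ten weeks.** The protocol abstract (section 1) says "Outpatient treatment will last 10 weeks and consist of thrice-weekly clinic visits", and places the cognitive testing "at repeated time points during the 10-week treatment". The dosing tables in section 6.4 and the assessment schedule in section 8 also end at week 10.
- **Nine weeks.** Section 7.2.3 says "During the 9-week treatment phase participants will be scheduled to attend three clinic visits per week (MWF", and section 7.2.5 says "At week 9, participants will be administered end of study assessments and given appropriate referrals to alternative treatment facilities in the area".
- **Twelve weeks.** The SAP, under primary hypothesis testing, says "Logistic regression will evaluate retention, defined by completion of 12 weeks of treatment, as function of intervention condition".

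Two outcomes depend on the length. Retention belongs to the SAP's hypothesis H1, alongside cocaine use. The abstinence endpoint comes from the abstract: "Secondary endpoints will include abstinence rates during the last 2 weeks of treatment, time in study, and medication compliance". It carries no week numbers, and the SAP text available does not mention it.

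The dosing tables label week 10 as run-down. Section 8 still schedules thrice-weekly urines in that week.

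**The concern.** A completion outcome has to be attainable on the schedule that participants follow. If the criterion is longer than the schedule, every participant has the same value and no treatment comparison exists. For retention this touches a stated part of H1.

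Replacing 12 by the scheduled length does not finish the repair, because the protocol gives both 9 and 10. A participant who leaves after week 9 but before the end of week 10 is a completer on one reading and a drop-out on the other. The censoring point for the proportional hazards analysis of time to drop-out moves in the same way.

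For abstinence, the two readings give windows that share only one week, and the week in which they differ at the end is the run-down week. Two analysts working from different sections could report different endpoints under the same name. If the choice is left open until the data are unblinded, it could be made with the results in view.

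**Working it through.** **1. Check of the one printed total tied to treatment length.** Table 1 in section 6.5 gives 180 prize draws. With full attendance, week *w* yields three visits of *w* draws plus 5 bonus draws, that is 3*w* + 5.

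- Weeks 1 to 9: 3 × 45 + 9 × 5 = 135 + 45 = 180, which reproduces the printed total.
- Weeks 1 to 10: 3 × 55 + 10 × 5 = 165 + 50 = 215.
- Weeks 1 to 12: 3 × 78 + 12 × 5 = 234 + 60 = 294.

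Table 1 prints visit numbers up to week 13 but leaves the draws blank after week 9. Its total fits nine weeks only.

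**2. Retention.** At three visits a week, 9, 10 and 12 weeks require 27, 30 and 36 visits. No dosing or assessment column exists after week 10. Counting the admission week in section 8 gives 11 weekly columns, still one short of 12. Read literally, completers number 0 in every arm. With 200 participants randomised equally to four arms (200 / 4 = 50), that is 0 of 50 in each. The odds are zero everywhere, and the odds ratio between any two arms is 0/0, which is undefined.

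**3. Abstinence window.** For treatment of length *T*, the final two weeks are *T* − 1 and *T*.

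| Reading | Window | Visits | Scheduled urines in run-down |
|---|---|---|---|
| 9 weeks | 8 and 9 | 22 to 27 | 0 of 6 |
| 10 weeks | 9 and 10 | 25 to 30 | 3 of 6 |
| 12 weeks | 11 and 12 | 31 to 36 | no dosing or assessment column exists |

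**4. What is planned in the weeks concerned.** Daily totals from the section 6.4 tables (levodopa in mg / ropinirole in mg):

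| Arm | Week 8 | Week 9 | Week 10 |
|---|---|---|---|
| Levodopa + ropinirole 4 mg | 800 / 4 | 800 / 4 | 400 / 2 |
| Levodopa + ropinirole 2 mg | 800 / 2 | 800 / 2 | 400 / 0 |
| Levodopa alone | 800 / 0 | 800 / 0 | 400 / 0 |
| Placebo | 0 / 0 | 0 / 0 | 0 / 0 |

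For the three adjacent steps in H2, the planned difference changes from week 9 to week 10 as follows:

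- 4 mg versus 2 mg: ropinirole 2 mg, then 2 mg (unchanged).
- 2 mg versus levodopa alone: ropinirole 2 mg, then 0 mg (no planned difference in week 10).
- Levodopa alone versus placebo: levodopa 800 mg, then 400 mg (halved).

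**5. Which reading the other sections support.** Sections 7.2.3 and 7.2.5, the last behavioral tasks at week 9 (section 7.2.4, Compensation Schedule) and the 180-draw total point to nine weeks. The abstract and the ten dosing columns point to ten. Section 8 also marks urines and prize draws in week 10, and has its only post-admission BDI-2 and BSCS there. That conflicts with end-of-study assessments at week 9 and with the blank week-10 draws in Table 1.

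**The case against.** The strongest reply is that the protocol can be read as nine weeks of treatment followed by one taper week, ten in all. The final two weeks of treatment are then weeks 8 and 9, both at maintenance, and the abstinence endpoint has no problem. This is a reasonable reading with the larger share of the supporting passages. It does not close the matter: the abstract calls all ten weeks treatment, and section 8 keeps end-type assessments and urines in week 10. It also does nothing for the 12-week definition.

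A second reply is that any analyst would notice the 12 and replace it. That is likely, but the replacement could be 9 or 10, and the plan should make that choice in advance.

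Third, the SAP cites a Sect. B.3.2.5.ii that was not available and may define abstinence. This stands as a limit on the endpoint part. It would not remove the conflict between the stated durations.

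A reader might infer more than the documents support:

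- **That half of the abstinence endpoint falls in run-down.** This holds only on the 10-week reading.
- **That the H2 test is compromised.** The SAP text does not say that the ordinal contrasts apply to this endpoint, and one of the three steps keeps its full planned difference in week 10.
- **That a loss of power can be computed from the dose reduction.** This would need assumptions about dose-linearity, carry-over and averaging across weeks that the documents do not give. Actual doses may also differ from plan, since the high-dose arm "has option to hold ropinirole dose at 2 mg/d if tolerability issues".
- **That retention cannot be analysed at all.** The time-to-drop-out analysis does not need the 12-week criterion, only a stated censoring point.

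**Conclusion.** The retention part holds without modelling assumptions: on the schedule supplied, 12 weeks exceeds the longest stated protocol duration by 2 weeks and the shorter one by 3. No participant can qualify as a completer, and the logistic regression has no variation to model. It is an internal inconsistency in an H1 outcome and should be corrected.

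The abstinence part is real but conditional. There are two candidate windows sharing only week 9, with 0 of 6 or 3 of 6 scheduled urines in run-down depending on which section is followed. It rests on the available text and could be settled by the section that was not supplied. Its effect on any treatment comparison cannot be sized from the documents. Nothing here bears on the validity of the primary outcome, the weekly mean proportion of days without cocaine use, which is not confined to the final two weeks.

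**What to change.** Before unblinding:

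1. Reconcile the 9-, 10- and 12-week statements across the protocol abstract, sections 6.4, 7.2.3, 7.2.5 and 8, Table 1 and the SAP. This review takes no position on which duration or dosing schedule is right.
2. Restate the SAP's retention definition so that it equals the scheduled treatment length, and give the matching censoring point for time to drop-out.
3. State the abstinence window by week number, say whether the run-down week counts as treatment, and either define abstinence or cite the section that does.

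One option for item 3 is to use weeks 8 and 9 and report week 10 separately. Both are maintenance weeks in the dosing tables, the choice agrees with sections 7.2.3 and 7.2.5, and 6 urines remain scheduled. Its downside is that, on the 10-week reading, it changes the endpoint rather than clarifying it, and week-10 results leave the main figure.

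The cost is an amendment to wording. No added visits, participants or assessments are needed.

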4. DESCRIPTION OF STUDY POPULATION

4.1 INCLUSION CRITERIA

1. be between 18 and 55 years of age
2. meet DSM-IV criteria for current cocaine dependence
3. have at least 1 positive urine benzoylecgonine (BE) specimen (> 300 ng/mL) during intake
4. be in acceptable health on the basis of interview, medical history and physical exam
5. be able to understand the consent form and provide written informed consent
6. be able to provide the names of at least 2 persons who can generally locate their whereabouts.

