7.2 STUDY SPECIFIC

7.2.1 ENROLLMENT/RANDOMIZATION

An urn randomization procedure will be used to assign subjects to one of the four treatment groups. This procedure will balance groups on important pretreatment characteristics that may influence measures of cognitive performance and/or treatment outcome. The variables will include (1) severity of cocaine dependence, based on days using cocaine in past 30; (2) baseline (trait) impulsivity score, based on the Barratt Impulsiveness Scale (BIS). The BIS was chosen as a variable for the urn randomization because it has norms for high and low impulsivity in cocaine users based on previous studies and has been predictive of treatment retention.

Treatment assignment will be concealed to all clinical and research staff, including the investigators. Only the study pharmacist who dispenses the study medication will be unblinded to participants' assigned condition.

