Cognitive-enhancing DA Medications for Cocaine Dependence

NCT01393457

Version Date: 09/02/2011

STATISTICAL ANALYSIS PLAN (SAP)

Data will be entered by research assistants into an existing, relational database (i.e. Microsoft Access). Data integrity will be maintained by restricting allowable input values on standardized Access entry forms. Double entry of a random subset of 10% of the observations will be used to identify problematic data entry issues. Preliminary data analyses evaluating group differences on demographic and baseline variables will use contingency tables with chi-square testing, ANOVA's, and examination of correlations between baseline variables and specified outcomes. Baseline or demographic variables, on which group differences are detected and which are correlated with outcomes, meet the definition of confounders and will result in two sets of analyses: one in which the relevant variable is included as a covariate and one in which it is not. This will permit determination of the degree to which any group differences might confound conclusions regarding treatment.

Broadly, the data analytic strategy will use generalized linear modeling and mixed effects models. Longitudinal analyses will be conducted using generalized linear mixed modeling (Proc GLIMMIX; SAS 9.2) for both continuous and discrete outcomes. Count, dichotomous and time to event data will be evaluated using Poisson (Proc GENMOD; SAS 9.2), logistic (Proc GENMOD; SAS 9.2), and proportional hazards regression (Proc PHREG; SAS 9.2) respectively. Distributional assumptions will be evaluated via inspection of residual plots and, where possible, by formal statistical tests. Violation of assumptions will be addressed, depending upon statistical technique, through the use of transformations, robust estimators, scaling coefficients, and stratification. Sample size approximations are obtained through empirical data simulation using SAS v.9.2.

PRIMARY HYPOTHESIS TESTING: To evaluate the efficacy of combination levodopa/carbidopa-ropinirole therapy in treatment of cocaine dependence. H1. The combination of levodopa/carbidopa and ropinirole will reduce cocaine use and increase treatment retention. H2. There will be a dose-response relationship such that

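### Pre-specify admit-week urine benzoylecgonine as a covariate in the cocaine-use analyses, rather than adjusting only when a baseline difference happens to be detected

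*Protocol*

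**What the plan says.** Protocol section 4.1 sets the urine criterion: participants must "have at least 1 positive urine benzoylecgonine (BE) specimen (> 300 ng/mL) during intake". Nothing in the protocol requires a positive specimen at randomisation or at first dose.

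Protocol section 7.2.1 describes an urn that balances characteristics thought to influence cognition or outcome: "The variables will include (1) severity of cocaine dependence, based on days using cocaine in past 30; (2) baseline (trait) impulsivity score". Urine status is not listed.

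The schedule in Protocol section 8 has "Urine rapid Test (3x/wk") marked in the admit week and in every treatment week, so a baseline urine value is already collected.

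The protocol abstract defines the endpoint: "The primary outcome measure will be weekly mean proportion of cocaine non-use days". It lists abstinence in the last 2 weeks among the secondary endpoints. In the SAP, "cocaine use will be measured by urine benzoylecgonine and by the SPRHK1 approach", and "Generalized linear mixed models will evaluate the probability of cocaine use as a function of time, treatment and their interaction". No baseline urine term is named.

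The SAP's general rule for baseline variables is conditional. A variable on which groups are found to differ, and which correlates with outcome, "will result in two sets of analyses: one in which the relevant variable is included as a covariate and one in which it is not". Neither set is called primary.

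**The concern.** A participant who is positive once early in intake and negative afterwards meets the criterion, as does one who is positive throughout. These two start treatment at different points on a measure close to the outcome, and that difference probably predicts later urine results. A count of use days over the past 30 cannot fully separate them, since it does not show whether use stopped after intake began.

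Two things are at stake. First, a strong predictor that is already measured is left out of the model, which costs precision. Second, whether it enters depends on a baseline comparison of the randomised arms. If it does enter, the reader gets two results with no rule for which one answers H1. In a logistic-type mixed model, adjusted and unadjusted odds ratios can differ even when arms are balanced, so the choice is not cosmetic.

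**Working it through.** **Inputs from the documents.** The ITT sample is 200 with equal allocation to four arms (Protocol abstract): 200 / 4 = 50 per arm. The plan gives no figure for the share of BE-negative starters or for the value of adjustment. The SAP says sample size came from simulation but gives no inputs, so one cannot tell whether baseline adjustment was assumed.

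**Assumptions.** Share BE-negative at start, q: 0.10 to 0.40. Extra proportion of non-use days in such participants, g: 0.3 to 0.4. Between-participant SD of the outcome, s: 0.35 to 0.40. None of these is in the documents.

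**Step 1: size of chance imbalance.** The SD of the difference between two arms is sqrt(2q(1 - q)/50). At q = 0.20 this is sqrt(0.32/50) = 0.080. The probability that two given arms differ by 5 or more such participants is the exact binomial value.

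**Step 2: would the SAP's rule act?** I simulated four arms of 50 under simple randomisation. The SAP names chi-square testing; I took the screen as a 3-df chi-square at 0.05, a level the SAP does not state. The last column is the share of cases flagged when two given arms differ by 5 or more.

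| q | SD of difference (points) | P(two arms differ by 5 or more of 50) | Flagged when they do |
|---|---|---|---|
| 0.10 | 6.0 | 13% | about 18% |
| 0.20 | 8.0 | 26% | about 12% |
| 0.30 | 9.2 | 33% | about 10% |
| 0.40 | 9.8 | 36% | about 10% |

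The conditional rule therefore leaves most imbalances of this size unadjusted.

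**Step 3: does balancing on past-30-day use remove it?** I idealise the urn as two equal strata of use, with exact balance. At q = 0.20, with BE-negative rates of 35% and 5% in the low- and high-use strata, the within-stratum variance is 0.5 × 0.35 × 0.65 + 0.5 × 0.05 × 0.95 = 0.1375. The SD is sqrt(2 × 0.1375/50) = 0.074, against 0.080 without balancing. With rates of 25% and 15% it is 0.079. The help is small.

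**Step 4: effect on an average level.** A 1-SD imbalance moves a comparison of arm levels by SD × g: from 6.0 × 0.3 = 1.8 points to 9.8 × 0.4 = 3.9 points. This is ordinary sampling variation, already counted in the standard error; adjustment would remove part of it.

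**Step 5: precision gained by adjusting.** The share of variance explained is q(1 - q)g²/s², and the equivalent arm size is 50/(1 - share).

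- q = 0.10, g = 0.3, s = 0.40: 0.09 × 0.09/0.16 = 0.051; 50/0.949 = 52.7.
- q = 0.10, g = 0.4, s = 0.35: 0.09 × 0.16/0.1225 = 0.118; 50/0.882 = 56.7.
- q = 0.20, g = 0.3, s = 0.40: 0.16 × 0.09/0.16 = 0.090; 50/0.910 = 54.9.
- q = 0.20, g = 0.4, s = 0.35: 0.16 × 0.16/0.1225 = 0.209; 50/0.791 = 63.2.

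So adjustment is worth about 3 to 13 participants per arm. This is a linear approximation for a comparison of levels, with urine reduced to two categories.

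**The case against.** The strongest reply is that the SAP already deals with imbalanced baseline variables and the urn already balances a baseline measure of use in days, which is close to the protocol's endpoint. Both points are true. What remains is that the rule depends on detection (step 2), that it names no primary result when it fires, and that past-30-day use is an incomplete stand-in for urine status (step 3).

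The second reply is that H1 tests differential change over time. A constant difference in level between participants cancels from a linear treatment-by-time term on the same scale, so steps 4 and 5 do not describe that test. This stands: the gain for the interaction could be much smaller than for levels, unless ceiling effects or different trajectories link starting status to slope. The level calculation does bear on abstinence in the last 2 weeks. The SAP also does not say whether the admit week is a time point in the model; if it is, starting status is already represented there.

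Third, prevalence is unknown. Intake runs under a separate protocol (Protocol section 7.1). The 90.2% baseline figure in Protocol section 6.2 is an average rate of positive urines in another cohort, not a share of participants. Nor do the documents say that the rapid test is the outcome assay, or define the SPRHK1 approach. These limits stand; they are why no firm size is given.

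**Conclusion.** The point holds as a free improvement. The plan collects a baseline urine measure close to its outcome but uses it only if a baseline comparison happens to flag it, and it then leaves two results of equal standing. The loss is some precision and a data-dependent choice of analysis. The illustrative size, 3 to 13 participants per arm for a level comparison, rests on an assumed prevalence of 10% to 20%, a gap of 30 to 40 points and an SD of 0.35 to 0.40.

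A reader might infer more than this. One inference is that imbalance in already-abstinent participants biases the primary contrast or creates a false drug effect. It does not: randomisation makes the comparison valid on average, and chance imbalance is part of the stated error. Another is that section 4.1 is faulty and should require a later positive. The documents do not support that either: preventing relapse fits the late-abstinence endpoint, and enrolling such participants is a design choice. A third is that the urn must add urine status. That is a debatable trade-off, since randomisation would have to wait for the last admit-week test, and a model term does most of the work.

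**What to change.** In the SAP, name admit-week urine BE as a fixed covariate in the primary cocaine-use model and in the model for abstinence in the last 2 weeks. A suitable form is the proportion of the scheduled admit-week specimens that are BE-positive, with a stated rule for missing specimens. Call the adjusted analysis primary whether or not a baseline difference is detected, and keep the unadjusted analysis as a sensitivity analysis. If the admit week is instead modelled as a time point, say so and do not also enter it as a covariate.

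A proportion is preferable to splitting participants into any-negative and all-positive groups. A single negative does not show that someone has stopped, and at q = 0.10 separate contrasts would rest on about 0.10 × 50 = 5 BE-negative participants per arm.

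The cost is a few sentences in the SAP and one model term. Eligibility, the urn, visits and the sample size of 200 stay as they are.
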